The endpoints to be measured in this study are described in Section 2.

Figure 1 Study Flow Diagram

ADA = anti-drug antibody; CHD = congenital heart disease; CLD = chronic lung disease; IM = intramuscular; PK = pharmacokinetic.

SEASON 1: Randomization for Season 1 Day 1, 2:1 MEDI8897 or palivizumab group

SEASON 2 (CLD/CHD cohort only): Randomization for Season 2 Day 1: Subjects who were randomized in Season 1 to receive MEDI8897 will receive MEDI8897 in Season 2.

Subjects who were randomized to receive palivizumab in Season 1 will receive MEDI8897 or palivizumab in Season 2

Blood samples for PK and ADA: Season 1 for both cohorts – Screening or Day 1 predose and on Days 31 (predose), 151, and 361 (for CLD/CHD cohort, prior to Season 2 dosing); Season 2 for CLD/CHD cohort only - Days 31 (predose), 151, and 361. Additionally, samples will be collected during both seasons from all subjects hospitalized for a respiratory infection, and before and after cardiac surgery with cardiopulmonary bypass for subjects with CHD requiring a replacement dose of study drug.

Safety assessments will be performed through Day 361 for each respective season.

^a In the MEDI8897 group Season 1, dose level will be stratified by body weight at time of dosing; subjects will receive 50 mg MEDI8897 if < 5 kg or 100 mg MEDI8897 if ≥ 5 kg.

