Vital signs	X ^c		X	X ^c	X ^c	X ^c	X ^c	X	X					X
Blood sample for PK, ADA, RSV neut Ab, and RSV serology ^d				X (pre-dose)				X	X			X ^e		X
Assessment of AEs/SAEs, AESIs, NOCDs	X	X	X	X	X	X	X	X	X	X	X	X	X	X
Concomitant medications	X	X	X	X	X	X	X	X	X	X	X	X	X	X
Randomization ^f	X													
Study drug administration ^g	X			X	X	X	X							

Table 6 Schedule of Treatment Period and Follow-up Period Study Procedures: Season 2, CLD/CHD Cohort Only

Study Period	Treatment Period							Follow-up Period						
Visit Number	V10 ^a	TC	V11	V12	V13	V14	V15	V16	V17	TC		LRTI	Skin Reaction	Replacement Dose Follow-up ^b
Procedure / Study Day	D1	D8 (± 2 days)	D15 (± 2 days)	D31 (± 2 days)	D61 (± 2 days)	D91 (± 2 days)	D121 (± 2 days)	D151 (± 7 days)	D361 (± 7 days)	D1-151 Q2W (± 5 days)	D152-361 monthly (± 5 days)	D1-361 as needed	D1-361 as needed	360 days post last replacement dose (± 7 days)
Assessment of LRTI or any respiratory infection that requires hospitalization												X ^c		
Nasal swab collection												X ^c		
Assessment of skin reaction													X ^h	
Telephone contact ⁱ		X								X	X			
HRU and caregiver burden ^j												X		

ADA = anti-drug antibody; AEs = adverse events; AESIs = adverse events of special interest; CHD = congenital heart disease; CLD = chronic lung disease; D = study day; ER = emergency room; HRU = healthcare resource utilization; ICU = intensive care unit; IM=intramuscular; LRTI = lower respiratory tract infection; neut Ab = neutralizing antibody; NOCDs = new onset chronic diseases; OTC = over-the-counter; PK = pharmacokinetic; Q2W = once every 2 weeks; RSV = respiratory syncytial virus; SAEs = serious adverse events; SID = subject identification; TC = telephone call; V = visit.

^a The Season 2 Visit 10/Day 1 (Dose 1) may be the same as the Season 1 Visit 9/Day 361.

^b Subjects who receive a replacement dose of study drug due to cardiac surgery with cardiopulmonary bypass will be followed for 360 days after the last replacement dose with the same schedule for telephone calls and a final visit 360 days post the last replacement dose.

^c All vital signs (temperature, blood pressure, heart rate, and respiratory rate) should be obtained within 60 minutes prior to dosing, and at 30 minutes (± 5 minutes) and 60 minutes (± 5 minutes) post dose.

Table 6 Schedule of Treatment Period and Follow-up Period Study Procedures: Season 2, CLD/CHD Cohort Only

Study Period	Treatment Period							Follow-up Period						

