4.3.8 Estimate of Volume of Blood to be Collected

Blood volume estimates are provided by visit/study day for Season 1 ([Table 9](#)) and Season 2 ([Table 10](#)).

Table 9 Volume of Blood to be Collected, Season 1

Visit/Study Day	Estimated Blood Volume (mL)
Visit 1/Screening or Visit 2/Day 1	1.5 mL
Visit 4 /Day 31	1.5 mL
Visit 8/Day 151	1.5 mL
Visit 9/Day 361	1.5 mL
Total	6.0 mL

Table 10 Volume of Blood to be Collected, Season 2

Visit/Study Day	Estimated Blood Volume (mL)
Visit 12/Day 31	1.5 mL
Visit 16/Day 151	1.5 mL
Visit 17/Day 361	1.5 mL
Total	4.5 mL

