- If there are 2 or more valid, non-missing observations within the same visit window, and
 - if they are on different days, then the non-missing one which is closest to the scheduled visit day will be used in the analysis.
 - if they are on the same day which is closest to the scheduled visit day, then the non-missing one with the later collection time will be used in the analysis.
- If 2 or more valid observations are equidistant from the scheduled visit, and
 - if they are on different days, then the non-missing observation with the earlier collection date will be used in the analysis for the post-baseline observations, and the non-missing observation with the later collection date will be used in the analysis for the screening observations.
 - if they are on the same day, then the non-missing observation with the later collection time will be used in the analysis.
- For LRTI visits or unscheduled visits, if 2 or more valid observations are collected on the same day, then the non-missing observation with the earlier collection time will be included in the analysis.
- If a visit window does not contain any observations, then the data will remain missing.
- For the visit-based summaries for ADA, if both ADA positive and negative samples are available within a subject's visit, ADA positive will be reported.

For assignment of data to adjusted analysis-defined visit windows, study day will be defined as:

- Screening period: Study day = Date of assessment date of randomization
- After randomization: Study day = Date of assessment date of randomization + 1

The adjusted analysis-defined windows for ADA, RSV neutralizing antibody, and RSV serology are defined in Appendix 2, and for clinical laboratory data are defined in Appendix 3.

The partial dates imputation rules are described in Appendix 4 and Appendix 5.

Categorical data will be summarized by the number and percentage of subjects in each category. Continuous variables will be summarized by mean, median, standard deviation, minimum, and maximum. In general, unless stated otherwise, baseline of each season will be defined as the last non-missing value within 30 days prior to the 1st dosing of the season. Baseline of Season 1 + Season 2 will be the same as baseline of Season 1.Data analyses will be conducted using the SAS® System Version 9.4 or higher (SAS Institute Inc., Cary, NC).

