3.7.1 Adverse Events and Serious Adverse Events

Adverse events and serious adverse events will be coded by MedDRA version 22 or higher and the type, incidence, severity and relationship to study investigational product will be summarized by treatment group. Specific AEs will be counted once for each subject for calculating percentages. In addition, the total number of AEs will also be provided. In addition, if the same AE occurs multiple times within a particular subject, the highest severity and level of relationship observed will be reported. All treatment-emergent AEs (TEAEs) and treatment-emergent SAEs (TESAEs) occurring through Day 361 will be summarized overall, as well as categorized by MedDRA SOC and PT. In addition, the TEAEs occurring at 1% or higher in either treatment group will be reported by PT.

Nontreatment-emergent AEs/serious adverse events (SAEs), defined as AEs/SAEs that occur prior to the administration of investigational product, or after Day 361, Season 1 for preterm cohort, or after Day 361, Season 1 and prior to Day 1, Season 2 for CHD/CLD cohort, or after Day 361, Season 2 for CHD/CLD cohort, or pre-planned surgeries that are coded with PT "Cardiac Operation" and occur during the study for CHD subjects will be presented in the listings.

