3.8 Anti-drug Antibodies

For each season as well as the two consecutive seasons (ie, Season 1, Season 2, Season 1 + Season 2) the summaries will be provided using the respective as-treated population. For Season 1, summaries of ADA to palivizumab and MEDI8897 will be provided for palivizumab and MEDI8897 group, respectively. The Season 1 summaries will also be provided for each cohort (pre-term, CHD/CLD). For Season 2, summaries of ADA to MEDI8897 will be provided for Palivizumab/MEDI8897 group only. For Season 1 + Season 2, summaries of ADA to palivizumab and MEDI8897 will be provided for

palivizumab/palivizumab and MEDI8897/MEDI8897 group, respectively. There is no intention to compare results of ADA to MEDI8897 and ADA to palivizumab.

The number and percentage of subjects who develop anti-MEDI8897 antibodies will be summarized at each visit by treatment group. For those with a positive assessment, the ADA titer results will also be summarized. The number and percentage of ADA positive samples with specificity to the YTE or RSV-neutralizing regions of MEDI8897 will also be summarized.

An additional table will summarize the number and percentage of subjects positive for ADA at baseline and positive at any post-baseline time point. The percentage who were persistent positive and transient positive will also be presented.

- Persistent positive is defined as negative at baseline and positive at ≥ 2 post-baseline assessments (with ≥ 16 weeks between first and last positive) or positive at last post-baseline assessment
- 2 Transient positive is defined as negative at baseline and at the last post-baseline assessment, and positive at ≥ 1 post-baseline assessment and not fulfilling the conditions for persistent positive.

To evaluate the impact of ADA on efficacy and safety, the efficacy endpoints (ie, incidence of medically attended RSV LRTI and RSV hospitalization), as well as TEAE and SAE by SOC and PT based on MedDRA will be summarized by ADA post-baseline status (ie, at least one post-baseline ADA positive or not through 360 days post 1st dose). The efficacy endpoints will also be summarized by ADA post-baseline status through 150 days post 1st dose.

The impact of ADA on PK will be evaluated as described in Section 3.9

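### The SAP's 30-day baseline limit does not fit Season 2 serum assays: the only scheduled pre-dose sample is Season 1 Day 361, which may be older than that

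*SAP*

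**What the plan says.** SAP 3.1 sets a general rule, to apply unless another is stated: "baseline of each season will be defined as the last non-missing value within 30 days prior to the 1st dosing of the season". It adds that "Baseline of Season 1 + Season 2 will be the same as baseline of Season 1".

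The protocol's sampling plan for Season 2 appears in three places, which agree:
- The notes to Figure 1 (Protocol 3.1.1) give the sampling days as "361 (for CLD/CHD cohort, prior to Season 2 dosing); Season 2 for CLD/CHD cohort only - Days 31 (predose), 151, and 361".
- In Table 6 (Protocol 4.2.2), the row "Blood sample for PK, ADA, RSV neut Ab, and RSV serology" is empty at Visit 10/Day 1. Its first mark is at Visit 12/Day 31, pre-dose.
- "Table 10 Volume of Blood to be Collected, Season 2" (Protocol 4.3.8) lists Days 31, 151 and 361 only.

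Footnotes to Tables 5 and 6 allow Visit 9 (Season 1 Day 361, ± 7 days) and Visit 10 (Season 2 Day 1) to be the same visit. They do not require it. SAP 3.7.1 has a class of non-treatment-emergent events that occur "after Day 361, Season 1 and prior to Day 1, Season 2 for CHD/CLD cohort", so the SAP foresees time between the two.

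On use of the baseline, SAP 3.6.3 and 3.6.4 plan geometric mean fold-rise for each season, and SAP 3.8 says: "For Season 2, summaries of ADA to MEDI8897 will be provided for Palivizumab/MEDI8897 group only".

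**The concern.** The 30-day limit suits Season 1, where screening runs from Day -30 to Day 1 and a sample is due at screening or before the first dose. Season 2 has no screening draw and no Day 1 draw. The baseline must come from a visit timed from Season 1 Dose 1, while Season 2 dosing is for children entering their second RSV season. Nothing keeps these two dates within 30 days of each other.

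If they drift further apart, the rule as written discards a valid pre-dose sample and leaves the infant with no Season 2 baseline. At stake are the Season 2 fold-rise summaries for two exploratory endpoints and part of one secondary endpoint, ADA in infants first given MEDI8897 in Season 2. If the gap is noticed only at the Season 2 analysis, the choice of baseline would be made after Season 1 treatment has been unblinded to the sponsor's analysis team.

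**Working it through.** **Step 1. Is there a Season 2 Day 1 draw?** Protocol 4.3.8 gives 1.5 mL per draw.
- Season 1: 4 draws × 1.5 mL = 6.0 mL, matching the Table 9 total.
- Season 2: 3 draws × 1.5 mL = 4.5 mL, matching the Table 10 total.

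A Day 1 draw would have made Season 2 4 × 1.5 = 6.0 mL. The stated total is therefore reproduced only without one.

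**Step 2. When is the baseline lost?** The last Season 2 dosing day with a valid baseline is the study day of the Visit 9 sample + 30, counted on the Season 1 calendar. Over the ± 7-day window:
- sample on Day 354: dosing up to Day 384;
- sample on Day 361: dosing up to Day 391;
- sample on Day 368: dosing up to Day 398.

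Dosing after that leaves no scheduled sample inside the 30 days. A sample taken at a hospitalization for respiratory infection could fill the gap by chance.

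**Step 3. Does another section override the default?** SAP 3.6.3, 3.6.4 and 3.8 name no other baseline. Appendix 2 gives these assays a Day 1 window of study day 1 or earlier, without a lower limit, but it assigns samples to visits and does not define baseline.

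**Step 4. Which results need the Season 2 baseline?**
- Serology fold-rise (SAP 3.6.4, expressly from baseline): yes, in all three groups.
- Neutralizing-antibody fold-rise (SAP 3.6.3, reference not named; I take it to be baseline): yes, in all three groups.
- Baseline ADA status, and persistent or transient positivity, both of which require a negative baseline (SAP 3.8): yes, but only in palivizumab/MEDI8897. The other two groups are reported over Season 1 + Season 2 with the Season 1 baseline.
- ADA positivity by visit, titers, and efficacy and safety by post-baseline ADA status: no.
- RSV exposure by a rise of at least 4-fold (SAP 3.6.4): no, since it is measured against the previous timepoint.
- PK (SAP 3.9): no, since concentrations are summarized by nominal time.

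**Step 5. Size.** The planned Season 2 groups are about 200 + 50 + 50 = 300 infants if all continue. One lost baseline in palivizumab/MEDI8897 is 1/50 = 2%. The documents do not say how many gaps exceed 30 days. Purely as an illustration, with an assumed share f:
- f = 5%: 15 of 300 for fold-rise, 2.5 of 50 for ADA;
- f = 10%: 30 and 5;
- f = 20%: 60 and 10;
- f = 30%: 90 and 15.

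**Step 6. What does an older sample cost?** Under first-order decay, a sample 30 days older is higher by a factor of 2^(30/half-life) in its drug-derived part.
- MEDI8897 (Protocol 1.4.1, median 56.5 days, range 46.8 to 81.1): 2^(30/56.5) = 1.44, with a range from 2^(30/81.1) = 1.29 to 2^(30/46.8) = 1.56.
- Palivizumab (Protocol 1.1, about 1 month): 2^(30/30) = 2.

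The MEDI8897 figures concern infants who had it in Season 1, and the palivizumab figure concerns the other two groups. Decay makes the baseline too high and understates fold-rise. An RSV infection between Visit 9 and Season 2 dosing works the other way, because its antibody rise would be counted as Season 2 fold-rise.

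**The case against.** The strongest reply is that the 30-day sentence is only a default and the rest of the plan points to Visit 9. The protocol marks that sample as taken before Season 2 dosing, the two visits are designed so that they can coincide, and the open Day 1 window in Appendix 2 would admit the sample. This shows what was probably intended. It does not supply the exception that the default calls for, and a programmer who follows SAP 3.1 would drop the value. At the least, the two rules can give different answers and must be reconciled.

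Other parts of the reply stand:
- A reader might infer that affected infants lose their ADA status in every group. SAP 3.8 does not support that (Step 4).
- A reader might infer that a sizeable share of infants is affected. SAP 3.7.1 shows that some gap is expected, not one over 30 days. Table 3 of the SAP also allows Season 2 dosing before Day 361, where no long gap arises.
- A reader might infer that the remaining infants form a biased subset. The gap plausibly follows the calendar date of first dosing, but nothing in the documents links it to antibody response.
- The limit has a purpose. It keeps drug decay and intervening infection out of the baseline, so an older sample is not free (Step 6).
- Appendix 2 refers to separate Japan and EU protocols. Their Season 2 sampling schedules are not among the documents reviewed and could differ.

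**Conclusion.** The mismatch is real and worth correcting before the Season 2 analysis. With no Season 2 Day 1 draw and no maximum gap after Visit 9, the default in SAP 3.1 removes the baseline of any infant dosed more than 30 days after that sample, unless another sample happens to fall in the window. The loss covers Season 2 fold-rise in neutralizing antibody and serology in all three groups, and baseline and persistent/transient ADA results in about 50 palivizumab/MEDI8897 infants, at 2% each.

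The number lost cannot be derived from the documents, and the shares in Step 5 are assumptions. The conclusion also assumes that the default governs these assays, since no exception is stated, and that the global protocol's schedule applies. The primary safety objective and the efficacy summaries are not affected. It would go too far to say that the Season 2 immunogenicity results are invalid or that ADA results fail generally: most ADA outputs, the exposure measure, PK and all two-season summaries remain intact.

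**What to change.** Add one sentence to SAP 3.1: for ADA, neutralizing antibody and serology, Season 2 baseline is the last non-missing sample before Season 2 Dose 1 taken at the Season 1 Day 361 visit (Visit 9) or later, without the 30-day limit. Flag baselines older than 30 days, and present Season 2 fold-rise with and without them. In Appendix 2, give the Season 2 Day 1 window the same lower bound, and state that the Visit 9 sample may serve both as Season 1 Day 361 and as Season 2 baseline. Keep the 30-day rule for Season 1 and for clinical measures. PK needs no change.

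The cost is that sentence, the Appendix 2 alignment and one extra display. No additional blood is needed. Losses from this cause fall to zero wherever a Visit 9 sample was taken before Season 2 dosing; infants with no such sample are not recovered. The downside is that older baselines carry the decay shown in Step 6, about 1.3- to 1.6-fold per 30 days for MEDI8897 and about 2-fold for palivizumab, and may precede an infection in the interval. Starting the look-back at Visit 9 bounds how old the sample can be, and the flagged display shows whether these baselines matter.

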3.2 Analysis Populations

The analysis populations are defined in Table 1.

Table 1Analysis Populations

Population	Description	
Intent-to-treat (ITT)	The ITT population (Season 1) includes all subjects randomized in Season 1. In this population, subjects will be analyzed according to their randomized treatment group in Season 1.	
population (Season 1)	The analysis for baseline/demographic characteristics, efficacy and HRU for Season 1 will be performed on this population.	
Intent-to-treat (ITT)	The ITT population (Season 2) includes all CHD/CLD subjects enrolled in Season 2. In this population, subjects will be analyzed according to their randomized treatment group through the two seasons (ie, in Season 1 and in Season 2).	
population (Season 2)	The analysis for baseline/demographic characteristics, efficacy, and HRU for Season 2 and/or through the two seasons (Season 1 + Season 2), will be performed on this population.	
	The As-treated population (Season 1) includes subjects who receive any investigational product in Season 1. In this population, subjects will be analyzed according to the actual treatment received in Season 1.	
	The analysis for safety, PK, ADA, serology, and RSV neutralizing antibody for Season 1 will be performed on this population.	
As-treated population	For subjects who accidentally receive both MEDI8897 and palivizumab in Season 1:	
(Season 1)	- For summaries on safety, subjects who receive any amount of MEDI8897 will be included in the MEDI8897 group.	
	 For summaries on PK, ADA, serology, and RSV neutralizing antibody, subjects will be analyzed according to the first dose they receive. The data collected up to the point of dose switch will be included in the summaries. All the data collected afterwards will be presented in the listing. 	
	The As-treated population (Season 2) includes subjects who receive any study investigational product in Season 2. In this population, subjects will be analyzed according to the actual treatment received through the two seasons (ie, in Season 1 and in Season 2).	
As-treated population (Season 2)	The analysis for safety, PK, ADA, serology, and RSV neutralizing antibody for Season 2 and/or through the two seasons (Season 1 + Season 2), will be performed on this population.	
	For subjects who received mixed doses of investigational product, similar rules as described above for Season 1 will be applied for Season 2.	

3.3 Stratification Factors

Two stratification factors are used in study design as well as in data analysis, and these are: age group at Season 1 randomization (age ≤ 3.0 months, age > 3.0 to ≤ 6.0 months, age > 6.0 months) and hemisphere (northern hemisphere, southern hemisphere). For subjects who were assigned to an incorrect age stratum at randomization, the age stratum as calculated from the electronic case report form (eCRF) will differ from the stratum recorded for the subject in the IWRS database. Unless stated otherwise, the age stratum based on the eCRF calculation will be used.

eCRF calculation for age when full date of birth (DOB) is available:

• Age at randomization (months) = $\frac{\text{randomization date} - \text{DOB}}{(365.25/12)}$

When full DOB is unavailable, age at screening will be used. Since screening may be collected in terms of days, weeks, or months, it will be first converted to months as follows:

- Age at screening (days) / (365.25/12) = Age at screening (months)
- Age at screening (weeks) / (52/12) = Age at screening (months)

Once age at screening is converted to months, then age at randomization will be obtained as follows:

• Age at randomization (months)= Age at screening (months) + [(randomization date – screening date) / (365.25/12)].

Determination of hemisphere in stratification and analysis is as follows: The sites have been grouped together by country into the following two hemispheres: Northern Hemisphere (Austria, Belgium, Bulgaria, Canada, Czech Republic, Estonia, Finland, France, Germany, Hungary, Israel, Italy, Japan, Latvia, Lithuania, Mexico, Poland, Republic of Korea, Russia, Spain, Sweden, Turkey, Ukraine, United Kingdom, and United States of America [USA]) and Southern Hemisphere (Argentina, Australia, Brazil, Chile, Colombia, New Zealand, Panama, and South Africa).

3.4 Study Subjects

3.4.1 Subject Disposition and Completion Status

Summaries will be presented by treatment group (as-randomized) for each season:

• Season 1: summary of subject eligibility and randomization as well as treatment received (including summary of subjects randomized but not treated, subjects who discontinued treatment) will be provided for all screened subjects. In addition, disposition of subjects throughout the study and by milestone visit (ie, Day 151, Day 361) will be provided.

These summaries will be provided for each cohort (pre-term, CHD/CLD) as well as for all subjects combined.

• Season 2: Similar summary as described above for Season 1 will be provided for all subjects enrolled in Season 2, with the exception of subject eligibility, which is not applicable for Season 2.

